14.3.2 Physical examination

Details of physical examination results at screening will be tabulated per body system with counts/ percentages by treatment group at screening.

Changes compared to previous physical examination will be tabulated by treatment group for each visit.

14.4 12-lead ECG

Number of patients with normal/abnormal clinically significant/abnormal not clinically significant investigator assessments of 12-lead ECG will be tabulated with counts/ percentages by treatment group, visit and time point.

Descriptive measures by visit for PR interval time (msec), QRS interval time (msec) and QT interval time (msec) will be presented by treatment group for each visit and time point.

For visits having pre-dose and post-dose measurements the change from baseline will be derived using the pre-dose value as baseline value for calculation of the difference to each post-dose measurement. For visits having no post-dose measurements the pre-dose value at visit V2 will be used as baseline. Tabulation will present descriptive statistics for change from baseline parameters by treatment group for each visit.

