Incidence calculated as percentage of baseline ADA-positive patients with significant increases (≥ 5 -fold) in ADA titer after drug administration and the total number of evaluable patients, excluding baseline-positive patients without any samples available after drug administration.

Secondary endpoints:

Characterization of ADA response:

- Incidence and titer of neutralizing activity of ADA positive patients
- Incidence of cross-reactivity of ADA positive patients towards endogenous glucagon
- Kinetics of ADA:
The timing and duration of detected ADA response

Safety:

- The incidence, type and severity of AEs
- Changes from baseline in clinical laboratory parameters
- Changes from baseline in vital signs
- Clinically meaningful changes from baseline in physical examination and electrocardiogram (ECG)

Exposure endpoints, after administration of first and third doses of trial medication:

- Plasma dasiglucagon and glucagon concentrations from 0-90 min after dosing will be evaluated based on the following endpoints: $AUC_{0-30\text{min}}$, $AUC_{0-90\text{min}}$, C_{max} , t_{max}

Pharmacodynamics after administration of first and third doses of trial medication:

- Plasma glucose profiles over the period from 0-90 min after dosing will be evaluated based on the following endpoints: $AUE_{0-30\text{min}}$, $AUE_{0-90\text{min}}$, CE_{max} , t_{max}
- Achieving a plasma glucose increase of ≥ 20 mg/dL within 30 minutes after treatment

7. Investigational plan

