7.3.2 Exclusion criteria

Patients meeting any of the following criteria during screening evaluations will be excluded from trial participation:

- (1) Previous administration of dasiglucagon (previously referred to as ZP4207).
- (2) Known or suspected allergy to trial medication(s) or related products
- (3) History of anaphylaxis or symptoms of severe systemic allergy (such as angioedema)
- (4) Previous participation (randomization) in this trial
- (5) Females who are pregnant according to a positive pregnancy test, actively attempting to get pregnant, or are lactating
- (6) Patients on a closed loop artificial pancreas
- (7) Receipt of any investigational drug within 3 months prior to screening
- (8) Active malignancy within the last 5 years
- (9) Congestive heart failure, New York Heart Association class II-IV

- (10) Inadequately treated blood pressure as defined as systolic blood pressure ≥ 160 mmHg or diastolic blood pressure ≥ 90 mmHg at screening.
- (11) Current bleeding disorder, including use of anticoagulant treatment
- (12) Known presence or history of pheochromocytoma (i.e. adrenal gland tumor) or insulinoma (i.e. insulin-secreting pancreas tumor)
- (13) Known or suspected HIV infection
- (14) Use of a systemic beta-blocker drug, indomethacin, warfarin or anticholinergic drugs in the previous 28 days before Day 1 of this trial)
- (15) Use of systemic corticosteroids, anti-inflammatory biological agents, kinase inhibitors or other immune modulating agents within the last 3 months prior to screening
- (16) Aspartate aminotransferase (AST) or alanine aminotransferase (ALT) >2.5 X the upper limit of normal (ULN), bilirubin >1.5 X ULN, estimated glomerular filtration rate (eGFR) <30 mL/min/1.73m² according to the Modification of Diet in Renal Disease (MDRD) Study definition. Altered electrolytes values of clinical relevance for cardiac conduction, as judged by the investigator.
- (17) Clinically significant abnormal ECG at screening, as evaluated by Investigator
- (18) Donation of blood or plasma in the past month, or in excess of 500 mL within 12 weeks prior to screening
- (19) A positive result in the alcohol and/or urine drug screen at the screening visit. Significant history of alcoholism or drug abuse as judged by the investigator or consuming more than 24 g alcohol per day for men, or more than 12 g alcohol per day for women.

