Trial material							
Administration of trial medication		X ⁹	X ⁹	X ⁹			

ECG = electrocardiogram; EoT = End of Trial; ; PD = pharmacodynamics; V = visit

¹ Informed consent can be obtained on the same day as screening, but prior to any trial-related procedures ² Pre-dose

³ Only check of changes between the screening visit and V2.

⁴ Coagulation parameters are measured at screening visit only. On dosing days Visit 2 and 4, blood samples are collected pre-dose, and at 30 and 90 min post-dosing. The actual time for sampling should not deviate from the nominal time by more than ± 5 min. Pre-dose is defined as within 5 min prior to dosing.

⁵ Local tolerability assessed at 0.5 and 2 h post-dose. The actual time for assessment should not deviate from the nominal time by more than ± 10 min.

⁶ Urine drug screen will be performed at trial site for visits 1-4

⁷ Pre-dose, 5, 10, 30, 60, and 90 min post-dosing. The actual time of blood sampling for exposure should not deviate from the nominal time by more than ± 1 min. Pre-dose is defined as within 5 min prior to dosing.

⁸ Pre-dose, 5, 10, 30, 60, and 90 min post-dosing. The actual time for blood sampling for plasma glucose should not deviate from the nominal time by more than ± 1 min. Pre-dose is defined as within 5 min prior to dosing.

⁹ Prior to administration of trial medication patients must reach a target plasma glucose level of 70-150 mg/dL. Plasma glucose levels may be adjusted by administration of a fast-acting insulin analog or by glucose ingestion at the discretion of the investigator. At visit 2 and 4 patients must be fasting for 90 min after administration of trial medication. At all dosing visits, patients will be treated individually to alleviate any potential side effects and will be observed for at least 5 h post-dose.

¹⁰ On dosing days Visit 2, 3 and 4 ECG's are assessed pre-dose, and at 20, 35, 45 and 60 min post-dosing. The actual time of assessment should not deviate from the nominal time by more than ± 5 min. Pre-dose is defined as within 5 min prior to dosing.

¹¹ Pregnancy test is only applicable for women of childbearing potential. At Visit 1 a serum pregnancy test should be performed. At Visit 2, 3 and 4 a pre-dose urine pregnancy test should be performed.

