13.1 Safety and tolerability endpoints

Safety and tolerability will be assessed by using the following endpoints:

1. The incidence, type and severity of AEs
2. Changes from baseline in clinical laboratory parameters
3. Changes from baseline in vital signs
4. Clinically meaningful changes from baseline in physical examination
5. Clinically meaningful changes from baseline in electrocardiogram (ECG)
6. Tolerability: Local tolerability in terms of skin reaction at 0.5h and 2h after post-dosing (note that local tolerability events are reported as adverse events as well)

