14.2 Routine laboratory

14.2.1 General

- High (H)/ Low (L) flags will be presented in laboratory listings, where appropriate. If normal ranges are not available, the flagging cannot be performed.
- All data will be listed in the clinical study report as raw data. For the summaries the most recent value will be used in case several measurements have been performed at one visit.

Tabulations will be prepared for each laboratory parameter by treatment group:

1. Laboratory results with continuous variables will be presented with descriptive statistics for each scheduled time point. They will be marked whether they are below (L), within or above (H) the respective reference range. The numbers in each category (above/below/within reference range) will be counted and percentages presented for each laboratory test result, visit and time point.
2. If laboratory values are categorical, the results (e.g. positive/ negative) will be presented with counts and percentages for each visit and time point available.
3. Presentation of 'change from baseline' values: Change from baseline will be evaluated for all laboratory parameters. The change will be calculated by building the difference between the pre-dose value and each post-dose measurement at each visit. Change from baseline values will be presented with descriptive statistics in case of continuous parameters. In case of categorical parameters shift tables will be presented.

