	14.3.3.3.2	Physical examination: Changes to previous visits	SAS	#LONG1 , #LONG2
	14.3.4	12-lead ECG		
	14.3.4.1	12-lead ECG: Abnormal findings	SAS	#LONG1 , #LONG2
	14.3.4.2	12-lead ECG: Descriptive statistics for PR interval, QRS interval and QT interval time	SAS	#LONG1 , #LONG2
	14.3.4.3	12-lead ECG: Change from baseline for PR interval, QRS interval and QT interval time	SAS	
	14.3.5	Previous and concomitant medication		
	14.3.5.1	Previous medication	SAS	#CONMED
	14.3.5.2	Concomitant medication	SAS	#CONMED
14.4		PHARMACOKINETIC (PK) AND PHARAMCODYNAMIC (PD) PROPERTIES		#LONG3
	14.4.1	Pharmacokinetics		
	14.4.1.1	Summary statistics of plasma dasiglucagon and GlucaGen concentration table	PKS	#PKCONC
	14.4.1.2	PK metrics	PKS	#PKMETRIC
	14.4.1.3	Figures: Mean analyte concentrations versus time – original scale	PKS	#PK_FDAY
	14.4.1.4	Figures: Individual analyte concentrations versus time curves- original scale	PKS	
	14.4.2	Pharmacodynamics		

	14.4.2.1	Summary statistics of plasma glucose concentration table	PKS	#PKCONC
	14.4.2.2	PD metrics	PKS	#PKMETRIC
	14.4.2.3	Figures: Mean concentrations versus time – original scale	PKS	#PK_FDAY
	14.4.2.4	Figures: Individual concentrations versus time curves- original scale	PKS	
14.5		STUDY DRUG ADMINISTRATION		
	14.5.1	Extent of exposure	SAS	#DESC
	14.5.2	Time between visits and total study duration	SAS	#DESC

List of data listings for analysis

ICH Heading	Listing Number	Listing Description	Comment
16.2		PATIENT DATA LISTINGS	
16.2.1		Discontinued patients	
	16.2.1.1	Trial termination form	
	16.2.1.2	Screening failures	
16.2.2		Protocol deviations	
	16.2.2.1	Protocol deviations	
	16.2.2.2	(Re-check of) Inclusion/ exclusion criteria	
	16.2.2.3	Check of dosing day exclusion criteria	
	16.2.2.4	Randomization	
16.2.3		Patients excluded from the efficacy analysis	
	16.2.3.1	Subject assignment to analysis populations	
16.2.4		Demographic data and baseline characteristics	
	16.2.4.1	Demographics	
	16.2.4.2	Medical history	
	16.2.4.2.1	General medical/ surgical history (incl. concomitant diseases)	
	16.2.4.2.2	Diabetes history	
16.2.5		Compliance and/or drug concentration data	
	16.2.5.1	Informed consent	
	16.2.5.2	Visit dates, number of visits at site, and study duration	
	16.2.5.3	Study drug administration	
	16.2.5.3.1	Assignment of trial medication	
	16.2.5.3.2	Total dose applied, number of days dosed, total duration of exposure	derived data
16.2.6		Primary endpoint, (key) secondary endpoints	

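### No planned ECG table shows within-patient change in the investigator's assessment or counts each patient once, although clinically meaningful ECG change is a named safety endpoint

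*SAP*

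**What the plan says.** SAP 13.1 lists "Clinically meaningful changes from baseline in electrocardiogram (ECG" among the safety endpoints, and protocol section 6 names the same endpoint together with physical examination.

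SAP 14.4 sets out the ECG analysis. The investigator classifies each tracing as normal, abnormal but not clinically significant, or abnormal and clinically significant, and the "investigator assessments of 12-lead ECG will be tabulated with counts/ percentages by treatment group, visit and time point". The PR, QRS and QT intervals get descriptive statistics and change from baseline. Baseline is the same-visit pre-dose value, or the Visit 2 pre-dose value for visits without post-dose readings.

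Appendix C has three ECG tables: 14.3.4.1, "12-lead ECG: Abnormal findings"; 14.3.4.2, interval descriptives; and 14.3.4.3, "12-lead ECG: Change from baseline for PR interval, QRS interval and QT interval time". Listing 16.2.7.6 gives the ECG data by patient.

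On the schedule, the flow chart in SAP section 4 states: "On dosing days Visit 2, 3 and 4 ECG's are assessed pre-dose, and at 20, 35, 45 and 60 min post-dosing". ECGs are also taken at Visits 5 and 7.

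For laboratory data, SAP 14.2.1 adds: "In case of categorical parameters shift tables will be presented". For physical examination, SAP 14.3.2 tabulates changes against the previous examination.

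**The concern.** The endpoint is a change within a patient. The only categorical ECG table is a set of cross-sections, one per visit and time point. A reader of the report could see how many patients were abnormal at 35 minutes after the second dose. That reader could not see how many patients in each arm had an assessment worse than their own pre-dose one, or how many had a clinically significant finding at any time. Two arms with identical rows could differ in the number of patients affected.

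For abnormal but not clinically significant readings there is a further loss. Equal counts before and after a dose could be the same patients, or some resolving while others newly appear.

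The omission is also out of step with the rest of the SAP, which plans a comparison with an earlier assessment for categorical laboratory results and for physical examination. SAP 14.4 never says what makes an ECG change clinically meaningful.

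**Working it through.** The plan states no figure on this point, so there is none to reproduce. The check counts the rows, compares the endpoint with the tables, and asks what the rows can tell us.

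**Rows.**
- Post-dose ECGs on dosing days: 3 visits (2, 3 and 4) × 4 times (20, 35, 45 and 60 min) = 12.
- Adding Visits 5 and 7: 12 + 2 = 14 scheduled rows, with the pre-dose rows shown separately.
- Protocol 7.5.6 makes the unscheduled ADA visit a repeat of Visit 4, dosing included. A patient with one such visit has 12 + 4 = 16 post-dose readings.

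**Endpoint against tables.**
- 14.3.4.1 has the category, but by row only. It has no comparison with pre-dose, no worst post-dose category and no any-time row.
- 14.3.4.2 has interval descriptives and no category.
- 14.3.4.3 has change from baseline, but for continuous intervals only, as group summaries.
- The LONG1 and LONG2 shells assigned to 14.3.4.1 are laid out by time or visit, and their notes describe quantitative statistics. Neither supplies a per-patient count.
- The SHIFT shell in Appendix D is for laboratory results and has only negative and positive categories.

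**What the rows can tell us.** The number of distinct patients is at least the largest single row count. Beyond that it depends on how far the rows overlap, which the table does not show.

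For illustration, take 112 / 2 = 56 patients per arm, one clinically significant patient in each of the 12 rows, and none pre-dose. The per-row count is an assumption. Every row then reads 1/56 = 1.8%.
- If the same patient recurs throughout: 1/56 = 1.8% of patients.
- If a finding persists through one visit, where readings are 15, 10 and 15 minutes apart, but a different patient is affected at each dose: 3/56 = 5.4%.
- Difference with identical rows: 2/56 = 3.6 percentage points.

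With the 45 completers per arm that the protocol targets, the two figures are 1/45 = 2.2% and 3/45 = 6.7%.

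Denominators may also differ between rows. SAP section 6 bases percentages on non-missing values, and the data review document (Table 1, item 5.1) treats a missed ECG as a minor deviation.

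**The case against.** The best reply is that this is a matter of display in a wholly descriptive trial whose primary endpoint is ADA incidence. The ECG endpoint asks for changes and not for an incidence. Protocol section 6 uses the word incidence for adverse events and does not use it here. A reader might infer that the endpoint expressly requires a patient count, and the wording does not go that far. What stands is narrower: whatever summary is chosen, it should show change within patients, and row counts of the category do not.

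Next, other outputs cover part of the gap. The adverse event definition in protocol 8.1 is broad enough to include an ECG finding, and SAP 14.1.3 counts a patient once per preferred term. Listing 16.2.7.6, sorted by treatment and patient, allows an exact count. Both points are fair but partial. The examples of adverse events in protocol 8.1 name clinically significant laboratory abnormalities and not ECG findings, nothing expressly requires a clinically significant ECG to be reported as an event, and a listing is not a summary.

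The exclusion of patients with "Clinically significant abnormal ECG at screening, as evaluated by Investigator" might also suggest that every clinically significant post-dose reading is new, leaving only de-duplication to do. That is unconfirmed. Table 1 of the data review document marks items 2.1 to 2.8 as having no findings, but leaves the comment on item 2.9, which covers this exclusion, blank. The blank does not show that such a patient was enrolled either.

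Finally, Amendment 1 added ECGs because of QTcB changes seen in phase 2. A reader might conclude that the planned tables would miss that signal and that a category shift table would catch it. The support is only indirect, because a table of overall category reflects QTc only where the investigator calls the tracing abnormal.

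**Conclusion.** The point holds as a modest gap. SAP 13.1 names a within-patient ECG change, and SAP 14.4 with its three tables cannot show one for the investigator's category or count each patient once. Adverse event tables may recover some clinically significant findings, and the listing recovers the rest by hand.

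The size is unknown because the documents give no ECG event rate. The 1.8% against 5.4% contrast rests on 56 patients per arm and an assumed one patient per row. With sporadic findings most rows would be zero and a hand count would be easy. A reader might push the same rows to 12 different patients (12/56 = 21.4%). That is arithmetically possible, but it needs readings 10 to 15 minutes apart to pick out a different patient each time, and nothing in the documents supports it.

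No conclusion on the primary endpoint is affected. This is an inexpensive improvement to consider.

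**What to change.** Add to SAP 14.4 one shift table by arm with three categories: normal, abnormal not clinically significant, and abnormal clinically significant.
- **Comparison:** same-visit pre-dose assessment to worst available post-dose assessment, for each dosing visit and over the three scheduled doses.
- **Overall panel:** enter each patient once, at the dosing visit with the greatest worsening. Ties go to the visit with the worse post-dose category.
- **Patient counts:** n (%) with any new clinically significant assessment at any of the three doses, defined as the clinically meaningful change, and n (%) with any worsening.
- **Missing readings:** include a patient with at least one post-dose reading at the visit, and footnote how many had fewer than four.
- **Visits 5 and 7:** use the Visit 2 pre-dose assessment as reference, as SAP 14.4 already does for the intervals.
- **Unscheduled ADA dosing visits:** show separately, since they add a dose and four more post-dose readings for selected patients.

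No new data are needed. The work is a worst-post-dose derivation, the missing-reading rule, and a SHIFT shell extended from two categories to three, with a panel for each visit. Appendix C lets minor changes to the table index go without a SAP amendment, but the definition of clinically meaningful change belongs in 14.4. If the table is added after database lock, SAP section 6 requires it to be labelled post hoc.

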4.5 Additional ECG assessment added

ECG will be measured at 20, 35, 45 and 60 minutes post dosing at all three dosing visits; 2, 3, and 4.

ZP4207-16136

Amendment 01, final version 1.0, 08-May-2017

The rationale for the change is due to the sporadic QTcB changes post dasiglucagon/GlucaGen administration observed in the phase 2 trial. The updated time points for ECG assessments are to cover the range of t_{max} for dasiglucagon and GlucaGen at all three dosing visits.

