The results of the phase 1 and 2 clinical trials confirm dose-proportionality for dasiglucagon pharmacokinetics, which is characterized by a fast absorption with a peak plasma concentration obtained after 35 minutes. Thereafter, the plasma concentration rapidly declines with an average half-life of 28 minutes. The median time to the maximum plasma concentration (C_{max}) was later for dasiglucagon than for GlucaGen (35 versus 20 minutes). Doses of 0.3 mg dasiglucagon and 0.5 mg GlucaGen and also 0.6 mg dasiglucagon and 1.0 mg GlucaGen were similar with regard to C_{max} . For C_{max} , the results indicated that 0.3 mg dasiglucagon was comparable to 0.5 mg GlucaGen (90% confidence interval (CI): 0.8167; 1.0068) and 0.6 mg dasiglucagon was comparable to 1.0 mg GlucaGen (90% CI: 0.8850; 1.1991).³ At these dose levels, the total exposures (AUC_{0-inf}) were higher for dasiglucagon compared to GlucaGen.

At all dose levels in the phase 2 trial, all patients achieved a plasma glucose level of at least 70 mg/dL as well as an increase in plasma glucose by at least 20 mg/dL within 30 min post-dose. The maximal observed time to reach the 20 mg/dL plasma glucose increase ranged from 15 to 27 minutes across doses and decreased as the dose increased. The pharmacodynamic responses of 0.6 mg of dasiglucagon and 1.0 mg of GlucaGen were comparable.³

Safety of dasiglucagon

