The safety data for dasiglucagon did not give rise to any relevant safety concerns for dasiglucagon beyond those related to the pharmacological effect of glucagon agonism. All adverse events (AEs) recorded in the trials were of mild or moderate severity. The most frequently reported systemic AE was nausea, which is a known side effect following administration of glucagon. Headache was the next most frequently reported event, occurring in all dose groups in the phase 2 trial. Injection site reactions were observed only sporadically after administration with either dasiglucagon or GlucaGen[®] and all were mild and transient. The most frequent injection site reaction was erythema, occurring in all treatment groups, including the placebo group, irrespective of dose. Glucagon has been described to exert positive inotropic and chronotropic effects and may therefore cause tachycardia and hypertension. In the phase 1 clinical trials, but not the phase 2 trial, temporary but clinically significant decreases in blood pressure were observed in a few healthy volunteers receiving investigational medicinal product (IMP) doses of at least 1.0 mg (4 with dasiglucagon and 1 with GlucaGen). This is not considered a safety concern, however hemodynamic changes post dosing will be considered a clinical event of interest.

The phase 1 and 2 results and the safety profile described to date do not give rise to specific safety concerns. For further information, please refer to the Investigator Brochure.³

Immunogenicity of dasiglucagon

To date, in the 3 clinical trials performed with dasiglucagon (described above), there have not been any anti-drug antibody (ADA) occurrences in a total of 141 subjects exposed to 1 or more doses. Data from the non-clinical toxicology program (7 non-clinical toxicity studies) showed that ADAs were detected in mice, rats, and dogs, and were most frequent in animals in the highest dasiglucagon dose groups. A fraction of the ADAs from rats and dogs were able to cross-react with native glucagon. However, the ADAs did not appear to be associated with changes in the safety or toxicity profiles compared to ADA-negative animals. In rats, the average exposure (AUC) was increased following 13 and 26 weeks of treatment in dose groups with higher ADA frequency (~ 8 mg/kg/day). The ADA frequency and titers of consistently ADA-positive rats were reduced from 13 to 26 weeks of treatment, indicating a transient response in most animals. It

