10.1.1 General considerations

All data obtained in this trial and documented in the eCRFs will be listed and summarized with statistics or frequency tables as appropriate. In case of termination of the trial, all data collected up to that time point will be included into the analysis.

Raw data listings and summary tables will be generated using the software SAS[®] Version 9 or higher.

All statistical analysis will be descriptive i.e. no formal testing will be performed.

Continuous variables will be summarized with means, standard deviations, medians, minimums, and maximums and valid cases.

Other summaries (e.g. quartiles, 95% confidence intervals) may be used as appropriate. Categorical efficacy and safety variables will be summarized by counts and by percentage of patients in corresponding categories.

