	16.2.6.1	Immunogenicity measurements	
	16.2.6.2	Antibody serum sample for immunogenicity measurements	
	16.2.6.3	Neutralizing antibody measurements (NAb titer)	
	16.2.6.4	Overall ADA incidence, treatment-induced ADA incidence, treatment boosted ADA-incidence	derived data

ICH Heading	Listing Number	Listing Description	Comment
	16.2.6.5	Kinetics: Timing and duration of detected ADA response	derived data
16.2.7		Adverse events and safety endpoints	
	16.2.7.1	Adverse events	
	16.2.7.1.1	Adverse events – CRF entries	
	16.2.7.1.2	Adverse events – MedDRA coding	
	16.2.7.1.3	Study-drug related adverse events (ADRs)	
	16.2.7.1.4	Serious adverse events	
	16.2.7.1.5	Deaths	
	16.2.7.1.6	Vital signs related to clinical events of interest	
	16.2.7.1.7	Injection site reactions	
	16.2.7.2	Local tolerability	
	16.2.7.3	Vital signs including change from baseline	incl. derived data CFB
	16.2.7.4	Body measurements	
	16.2.7.5	Physical examination and changes	
	16.2.7.6	12-lead ECG including change from baseline	
	16.2.7.7	Previous and concomitant medication	
16.2.8		Laboratory	
	16.2.8.1	Hematology including change from baseline	incl. derived data CFB
	16.2.8.2	Biochemistry including change from baseline	incl. derived data CFB
	16.2.8.3	Coagulation	
	16.2.8.4	Urinalysis including change from baseline	incl. derived data CFB
	16.2.8.5	Child bearing potential and pregnancy test	
	16.2.8.6	History of alcohol or drug abuse, alcohol breath test and urine drug screen	
16.2.9		Pharmacokinetics and pharmacodynamics	
	16.2.9.1	Plasma dasiglucagon and GlucaGen measurements	
	16.2.9.2	Individual PK metrics	derived data
	16.2.9.3	Plasma glucose measurements	
	16.2.9.4	Individual PD metrics	derived data
16.2.10		Comments	

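### SAP 14.4 summarises only uncorrected QT, although phase 2 QTcB changes prompted the dosing-day ECG schedule; QTcF and QTcB should be added if ECG heart rate was captured

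*SAP*

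**What the plan says.** SAP 14.4 plans two things for the ECG: a table of the investigator's overall assessment (normal, or abnormal with or without clinical significance), and interval summaries. On the latter, "Descriptive measures by visit for PR interval time (msec), QRS interval time (msec) and QT interval time (msec) will be presented" by treatment group, visit and time point, with change from the pre-dose value. In SAP Appendix C, Table 14.3.4.2 covers the interval values and Table 14.3.4.3 is titled "12-lead ECG: Change from baseline for PR interval, QRS interval and QT interval time". No corrected QT appears in the SAP text or the table list.

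Amendment 1, section 4.5, puts ECGs at 20, 35, 45 and 60 minutes after dosing at all three dosing visits. It gives the reason as "due to the sporadic QTcB changes post dasiglucagon/GlucaGen administration observed in the phase 2 trial" and says the times were chosen to cover t_max of both products. Section 4.4 of the amendment gives the same QTcB reason for excluding users of QT-prolonging drugs.

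Protocol version 3, section 7.6.4.2, names PR, QRS and QT among the ECG details to be recorded. The list is open-ended and mentions neither ECG heart rate nor RR.

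**The concern.** The observation that helped prompt the ECG schedule was a rate-corrected one. The quantity the SAP will tabulate is not. That would matter little if heart rate stayed still after dosing, but Protocol 5.1 says "Glucagon has been described to exert positive inotropic and chronotropic effects and may therefore cause tachycardia and hypertension". Protocol 8.1 also lists bradycardia among the signs that can mark a haemodynamic event of interest. A rising rate shortens raw QT and can hide a QTc increase; a falling rate does the opposite.

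Each fully dosed patient has 3 visits x 5 recordings (pre-dose and four post-dose) = 15 scheduled dosing-day ECGs. As planned, the interval tables built from them cannot by themselves show whether the phase 2 QTcB finding recurred.

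**Working it through.** The plan states no figure here that could be reproduced. The check has two parts: how far raw QT can depart from corrected QT, and whether other planned data fill the gap.

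**1. Size of the distortion (illustration)**

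Formulas: RR = 60/HR (seconds); QTcF = QT/RR^(1/3); QTcB = QT/RR^(1/2).

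Assumptions, none of them from the documents: pre-dose HR 70 bpm and QT 400 ms. Ranges are over HR 60, 70, 80 bpm and QT 360, 380, 400, 420 ms.

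Pre-dose: RR = 60/70 = 0.857, QTcF = 421.1 ms, QTcB = 432.0 ms.

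Post-dose raw QT = (421.1 + change in QTcF) x RR^(1/3). For example, with QTcF up 10 ms and HR up 5 bpm, RR = 60/75 = 0.8 and RR^(1/3) = 0.928, so QT = 431.1 x 0.928 = 400.2 ms, a raw change of +0.2 ms.

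Within-arm raw QT change:

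| HR change (bpm) | QTcF unchanged (ms) | QTcF +10 ms (ms) | Range for QTcF +10 |
|---|---|---|---|
| -5 | +10.0 | +19.7 | 17.1 to 22.7 |
| 0 | 0.0 | +9.5 | 9.1 to 10.0 |
| +5 | -9.1 | +0.2 | -1.3 to +1.7 |
| +10 | -17.4 | -8.3 | -11.5 to -5.1 |

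Between-arm raw QT difference, with a true QTcF change of +10 ms in the test arm and 0 in the reference arm:

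| HR change, test / reference (bpm) | Calculation | Result (ms) | Range |
|---|---|---|---|
| +10 / +10 | -8.3 - (-17.4) | +9.1 | 8.7 to 9.5 |
| +10 / +5 | -8.3 - (-9.1) | +0.8 | -0.5 to +2.1 |
| +5 / +10 | +0.2 - (-17.4) | +17.6 | 15.6 to 19.7 |

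The concurrent arm therefore works when rate changes match, and fails in either direction when they differ by 5 bpm.

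QTcB has its own weakness. With QTcF unchanged and HR up 10 bpm, raw QT is 400 - 17.4 = 382.6 ms and RR = 60/80 = 0.75, so QTcB = 382.6/0.75^(1/2) = 441.8 ms. That is a rise of 9.7 ms (8.2 to 10.9) from rate alone. The phase 2 QTcB changes could partly be rate artefact, which is why QTcF is the more useful addition.

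**2. Can vital-sign pulse stand in for ECG heart rate?**

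Times and windows are from footnotes 10 and 12 of the flow chart in SAP section 4; all windows are ±5 minutes. Post-dose pulse is taken at 30, 90 and 120 minutes. Pre-dose, both measurements fall in the same 5-minute window.

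| ECG (min) | ECG window | Nearest pulse window | Overlap |
|---|---|---|---|
| 20 | 15-25 | 25-35 | touches at 25 only |
| 35 | 30-40 | 25-35 | 30-35 |
| 45 | 40-50 | 25-35 | none |
| 60 | 55-65 | 25-35 or 85-95 | none |

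Only the 35-minute ECG has a usable pulse nearby. A proper correction at all four times needs heart rate or RR captured with the ECG itself.

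**The case against.** The strongest case is that this is a preference and not a defect. The protocol names PR, QRS and QT, and the SAP summarises those three. The ECG endpoint is clinically meaningful change, which the investigator assessment table addresses directly. The QTcB reference sits only in the amendment rationale, which calls the changes sporadic and attributes them to both products. Protocol 5.1 says "The phase 1 and 2 results and the safety profile described to date do not give rise to specific safety concerns". SAP 14.3.1 will tabulate pulse and its change from pre-dose by arm, so a reader will see at 30 minutes, close to dasiglucagon's median t_max of 35 minutes, whether heart rate moved and whether it moved differently between arms. Listing 16.2.7.6, "12-lead ECG including change from baseline", is not limited to three intervals, and Protocol 10.1.1 says "All data obtained in this trial and documented in the eCRFs will be listed and summarized with statistics or frequency tables as appropriate". Every bpm change used above is assumed.

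Much of this stands: no commitment is broken, the safeguards are real, and the size is unknown. A difference in plasma t_max (35 versus 20 minutes) does not prove a difference in heart-rate response; it only means that equal rate changes at a given time point cannot be taken for granted.

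It does not close the gap. The investigator assessment is categorical and has no stated QTc criterion. The pulse table is near only one of the four post-dose ECG times. A listing is not a summary. None of these gives a rate-corrected QT result by arm and time point.

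**Conclusion.** The point holds as a cheap improvement to a descriptive secondary safety summary. It is neither a contradiction of the protocol nor a threat to the primary ADA endpoint. If heart rate changes after dosing, the planned tables cannot separate rate from repolarisation. Under the assumed baseline, a rise of 5 bpm is enough to cancel a true 10 ms QTcF increase within an arm. With no rate change, raw QT is adequate.

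The actual size cannot be determined, because the documents give neither a baseline QT nor a post-dose heart-rate change. Whether the improvement is possible depends on what eCRF version 4.0 (cited in SAP section 2 but not available here) records with the ECG.

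**What to change.** Check whether heart rate or RR was captured with the ECG.

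- **If it was:** add QTcF, QTcB (only for continuity with phase 2) and ECG heart rate to Tables 14.3.4.2 and 14.3.4.3. Show value and change from pre-dose by treatment, visit and time point, and keep raw QT as supportive. The cost is a few derived variables and extra columns in two existing tables. Protocol 10.1 allows SAP adaptations before unblinding; under SAP section 6, anything added after database lock would be labelled post hoc.
- **If it was not:** state in the report that the raw QT summaries do not address the phase 2 QTcB observation. The cost is one sentence.

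Neither route needs a new patient procedure or a re-reading of tracings.
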